DESIGN Feasibility study/ Basic science study involving procedures with human volunteers

AIMS

- Investigating physiological changes during eating behaviours.
- Identifying physiological biomarkers for dietary behaviours and glycaemic outcomes.

OUTCOME MEASURES The primary outcome is the physiological features associated with dietary events (pre- vs post- meal).

Secondary outcomes include:

- Physiological and motor features associated with energy intake (high vs. low calorie meals).
- Physiological and motor features associated with glycaemic biomarkers, including blood glucose, insulin and hormonal levels

POPULATION Healthy adults

ELIGIBILITY Subjects aged 18-65 years with BMI of 18-30 kg/m² and no significant health problems.

DURATION Each participant will participate in two 2-hour study visits within up to 8 weeks

1. INTRODUCTION

1.1. BACKGROUND

Assessing dietary intake across populations is a fundamental challenge in nutrition research. Traditional dietary assessment methods, such as food diaries, rely on self-reporting of individuals and suffer from poor accuracy and recall bias. Food records are estimated to cause 11-41% underestimations for energy intake (Burrows et al., 2019). Furthermore, traditional methods are labour- and time- intensive and requires participants to manually record their food intake (Shim et al., 2014). Adherence dietary self-reporting is challenging even with mobile-based applications e.g., MyFitnessPal (Cordeiro et al., 2015).

Wearable sensing technology is emerging to ease the procedure of food intake assessment. The most popular technique is accelerometer-based system, which captures eating gestures via monitoring wrist motions that correspond to the hand-to-mouth movements during eating (Bell et al., 2020, He et al., 2020). The advantages include its simple structure and ability in capturing eating episodes and detecting time, speed, and duration of eating. However, this system cannot provide information about the energy intake and how food affects physiological response after meal. This knowledge is essential for determining the interaction between diet and health.

Food intake and digestion increases metabolism, body temperature and intestinal oxygen consumption. Elevated skin temperature, increased pulse rate/ heart rate and lowered oxygen saturation are observed during or after meals (Westerterp, 2004, Sit and Chou, 1984, Sidery and Macdonald, 1994, Cassiani et al., 2011); the rise of pulse rate has significantly correlated to meal size ($r = 0.990$; $P = 0.008$) in six healthy volunteers (Parker et al., 1995). This raises the possibility of using these physiological responses as potential indicators of food and energy intake (Amft and Troster, 2009). One major problem is that the relationships can be altered by confounders such as exercise, while this challenge may be overcome by incorporating physiological parameters with existing motor sensors, which recognized eating episodes with F-scores of 76.1% in precision and recall rates (Thomaz et al., 2015). It is hypothesized that integrating and physiological parameters and existing motor sensors may provide an objective tool for both detecting eating movement and estimating food consumption.

Our project aims to investigate the relationships between physiological responses and food and energy intake. Importantly, these physiological parameters can be measured using readily available, cost-effective sensors and products (e.g., smartwatch); thus, our findings may promote an accelerated development of a wearable tool for dietary assessment in future.

2. RATIONALE FOR CURRENT STUDY

Primary objective:

to investigate the feasibility of monitoring dietary behaviours by tracking physiological changes such as skin temperature, blood oxygen saturation, pulse rate and heart rate?

Secondary objectives:

- To examine the association between these physiological features and energy loads (high vs. low-calorie meals).
- To explore the relationship between these physiological features and glycaemic biomarkers, including blood glucose levels, insulin levels, and hormonal levels.

3. STUDY METHODOLOGY

3.1. PARTICIPANTS

10 healthy male and female participants. This is a pilot study in a new area and therefore a formal power calculation is not possible.

3.2. RECRUITMENT

Participants will be recruited from existing healthy volunteer databases and by advertisement in public places. Adverts will be placed in newspapers and put up in public buildings. A contact number on the advert will enable potential participants to contact the research team at Imperial College London. Participation in the study will be entirely voluntary. No undue influence will be exerted by the researchers. Participants will be free to withdraw from the study at any time.

3.3. STUDY DESIGN

Number of subjects: 10

Pre-Screening Questionnaire :

A pre-screening questionnaire considering the inclusion and exclusion criteria (see [section 3](#)) will be completed to establish eligibility. For subjects who complete the questionnaire but do not continue to participate, their data will not be saved. Participants will have a minimum of 48 hours to consider participation before providing consent.

Informed Consent: All participants will sign informed consent before starting the study (at the beginning of the 1st main study visit).

Main Study Visits:

Ten healthy subjects will attend two study visits at Clinical Research Facility. They will consume a high- and low-calorie meal designed by nutritional researchers, in a randomised order. Randomization will be performed using the 'sealed envelope' website by an independent researcher (i.e., not linked to the study). During eating events, physiological changes such as skin temperature, blood oxygen saturation, pulse rate etc and eating movements will be measured via a CE marked bedside monitor (Philips Healthcare) and non-invasive, wearable sensors. Blood samples will be taken at pre-determined time-points, starting 5 minutes before the meal and lasting for 60 minutes postprandially (at -5, +15, +30, +45, +60 min). A total of 25 ml blood will be taken per visit.

Sensor Data Acquisition and Recording

Participant will be invited to wear a multi-sensor monitor (please see the appendix 1 for the diagram) and recording of physiological and activity data during eating. Sensors on the monitor include:

- **Skin Surface Temperature Sensors:** Integrate skin surface temperature sensors to monitor changes in skin temperature during eating events. This data will provide insights into metabolic responses to food intake.
- **Pulse Rate Sensors:** Employ commercial pulse rate sensors, to continuously monitor participants' heart rates. Variations in pulse rate can indicate the intensity of eating episodes and physiological responses to food.
- **Oxygen Level Sensors:** Integrate oxygen level sensors, such as pulse oximeters, to measure blood oxygen saturation levels during eating events. Changes in oxygen levels can provide valuable information about participants' respiratory patterns and metabolic responses to food.
- **Blood Glucose Sensors:** The multi-sensor monitor will be equipped with non-invasive blood glucose sensors to continuously measure and record participants' blood glucose levels during eating episodes. This data is pivotal for understanding the impact of different foods on blood sugar regulation and insulin responses in individuals.
- **Movement Measurement Sensors:** Inertial Measurement Units (IMU) and accelerometers will be used to track the posture and movement of participants' hands during tests and to record the features of eating behaviours.
- **Force sensors:** The wearable monitor will include force sensors to monitor the wearing status (tightness) of the sensors themselves. Ensuring that the sensors are securely fastened is essential to maintain data accuracy. Force sensor data will serve as a quality control mechanism to guarantee that the sensors remain in optimal contact with the skin throughout the testing period.

Duration

End of the trial will be the last visit of the last participant in the study. The duration of each participant's involvement with the study will be up to 8 weeks.-Participants will be part of the study for two separate visits. Each visit will last for no more than two hours.

3.4. STUDY OUTCOME MEASURES

The primary outcome is the physiological features associated with dietary events (pre- vs post- meal).

Secondary outcomes include:

- Physiological features associated with energy intake (high vs. low calorie meals).
- Physiological features associated with glycaemic biomarkers, including blood glucose, insulin and hormonal levels

4. INCLUSION/EXCLUSION CRITERIA

4.1. INCLUSION CRITERIA

- Male or female
- Age between 18-65 years (inclusive)
- Body mass index (BMI) of 18-30 kg/m²
- Willingness and ability to give written informed consent.
- Willingness and ability to understand, to participate and to comply with the study requirements

4.2. EXCLUSION CRITERIA

- Outside of specified age and BMI range
- Chronic medical conditions including for eating disorders, diabetes, obesity, hypertension, cancer, acute infectious disease, renal disease, cardiovascular disease, and chronic gastrointestinal condition.
- Taking part in another research study or donating any blood in the last 3 months

4.3. WITHDRAWAL CRITERIA

Each participant has the right to withdraw from the trial at any time. In addition, the Investigator may discontinue a participant from the trial at any time if the Investigator considers it necessary for any reason including:

- An adverse event which requires discontinuation of the trial application or results in inability to continue to comply with trial procedures.
- Loss of capacity to consent. The only reason a participant may be withdrawn from study follow-up is in the event of withdrawal of consent, loss of capacity to consent or an adverse event which in the opinion of the Investigator was related to the study. Participants that are withdrawn from the study will be replaced by eligible participants. If a patient withdraws consent or loses capacity such that they are unable to consent to continue in the study then data collected up until that point will still be used in the analysis. Reason for not completing the study will also be collected. Further information will not be collected from patients who have withdrawn from the study.

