5.2. REPORTING PROCEDURES

All adverse events should be reported. Depending on the nature of the event the reporting procedures below should be followed. Any questions concerning adverse event reporting should be directed to the Chief Investigator in the first instance.

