6. ASSESSMENT AND FOLLOW-UP

There will not be follow-up visits. However, participants will be contacted via emails after study visits to identify incidental cases. Incidental cases will be reported to the GP.

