8.2. CONSENT

Consent to enter the study must be sought from each participant only after a full explanation has been given, an information leaflet offered and time allowed for consideration. Signed participant consent should be obtained. The right of the participant to refuse to participate without giving reasons must be respected. After the participant has entered the study, the clinician remains free to give alternative treatment to that specified in the protocol at any stage if he/she feels it is in the participant's best interest, but the reasons for doing so should be recorded. In these cases the participants remain within the study for the purposes of follow-up and data analysis. All participants are free to withdraw at any time from the protocol treatment without giving reasons and without prejudicing further treatment.

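### Does Protocol section 4.3 leave the data of a participant withdrawn for a study-related adverse event in dispute?

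*Protocol*

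**What the plan says.** Section 4.3 limits withdrawal from follow-up to three reasons. The third is "an adverse event which in the opinion of the Investigator was related to the study". The rules that follow differ in scope:

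- **Replacement** covers every withdrawal: "Participants that are withdrawn from the study will be replaced by eligible participants".
- **Data already collected** are dealt with in a sentence that opens "If a patient withdraws consent or loses capacity such that they are unable to consent to continue in the study" and concludes that "data collected up until that point will still be used in the analysis". The adverse-event reason is not named there.
- **Reason for not completing** is recorded.
- **Later collection** is closed: "Further information will not be collected from patients who have withdrawn from the study".

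Three other sections bear on the point. Section 5.2 says "All adverse events should be reported". Section 6 plans no follow-up visits but says "participants will be contacted via emails after study visits to identify incidental cases", without mentioning withdrawn participants. Section 8.2, on a clinician who gives treatment other than that in the protocol, says "In these cases the participants remain within the study for the purposes of follow-up and data analysis".

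**The concern.** Naming two of three reasons in the retention sentence invites the inference that the third is handled differently. If so, the participant whose consent is intact would be the one whose earlier data have no stated use. The primary outcome is a pre-meal versus post-meal comparison, so a single completed visit gives a usable record even if the second visit never takes place. Because everyone withdrawn is replaced, such a record would sit beside a full set of 10 completers, and whether to include it might be decided after the data are seen.

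There is also a safety side. Under section 4.3 an adverse event leads to withdrawal from follow-up only if it is judged related to the study. A bar on further information could then fall on the events whose course matters most. That would sit badly with the reporting duty in section 5.2 and the e-mail contact in section 6. Section 8.2 seems at first to give the opposite instruction, keeping participants in for follow-up and analysis.

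**Working it through.** The protocol states no figure to reproduce. Section 3.1 sets 10 participants without a power calculation and gives no dropout rate. The check is mainly a comparison of the texts.

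**1. Are adverse-event data excluded?** Section 4.3 contains no word such as *only* and no instruction to drop data. It affirms use in the two situations where permission to use the data is most open to doubt. If data are kept there, the argument for keeping them is stronger where the participant still consents and has capacity. The text is silent, and the silence has one natural completion.

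**2. Whom does the bar on further information cover?** Section 4.3 opens with the participant's own right to leave, then separately gives the investigator a power to discontinue a participant. The replacement sentence uses the passive (people who are withdrawn). The bar uses the active (people who have left). Read that way, the bar applies to those who leave by choice, and most of the friction with sections 5.2 and 6 disappears. The wording does not compel this reading, but it supports it.

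**3. Is the causal event lost?** The event comes before the withdrawal it causes. Section 5.2 requires it to be reported, the serious-event subsection (numbered 4.3.2) sets reporting times of 24 hours and 15 days, and section 4.3 records the reason for not completing. Only the later course of the event could go unrecorded, and only on the wider reading of the bar.

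**4. Does section 8.2 contradict section 4.3?** Section 8.2 concerns a participant given alternative treatment who stays in the study; its next sentence deals with withdrawal separately. It does not mention adverse events. The two sections meet only if an adverse event leads both to alternative treatment and to withdrawal, a case neither describes.

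**5. Does section 6 contradict section 4.3?** It describes an e-mail to find incidental cases for report to the GP. It says nothing about withdrawn participants or the use of their data. The tension is loose.

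**6. Size, by counting.** With *w* such withdrawals, each after one usable visit and each replaced, there are 10 completers plus *w* partial records.

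- Share of participants in question: *w*/(10 + *w*). For *w* = 1, 1/11 = 9%; for *w* = 2, 2/12 = 17%.
- Share of meal records for *w* = 1: completers give 10 × 2 = 20, so 1/21 = 4.8%.

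**7. How likely?** The protocol gives no risk, so 2%, 5% and 10% per person are assumptions. The chance of at least one such withdrawal in 10 is 1 − (1 − p)^10 = 0.18, 0.40 and 0.65. The chance of two or more is 1 − (1 − p)^10 − 10p(1 − p)^9 = 0.016, 0.086 and 0.26. These overstate the chance of a disputed record, which also needs a usable visit before the withdrawal.

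**8. Effect on the estimate.** Suppose, again as an assumption, that the partial record differs from completers by 1 to 3 SD. Weighted by person, the mean moves by 1/11 to 3/11, or 0.09 to 0.27 SD; weighted by meal, by 1/21 to 3/21, or 0.05 to 0.14 SD. The 95% half-width with 10 people is 2.262/√10 = 0.72 SD. Nothing in the protocol supports a difference of that size. A first-visit record completed before the event would not have been distorted by it; a distorted record would not be the valid contrast on which the concern relies.

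**The case for a change.** The strongest case for a change is that the protocol does not leave this matter wholly to a later document. It sets a rule for data use on withdrawal and covers two of its own three reasons. Whether staff may contact someone after withdrawal is a matter of conduct, which an analysis plan cannot repair afterwards. With 10 participants one record carries visible weight, and clarifying it would take only two sentences.

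Some of this stands. The retention sentence is incomplete, and the bar does not say whether it reaches participants withdrawn by the investigator. The reading limited to self-withdrawal eases the second point but does not settle the first.

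It still falls short of a reason to change the plan. No stated rule, applied as written, gives a wrong result. Which partial records enter an analysis is usual content for a statistical analysis plan. That plan is not available here, so it cannot be assumed that the choice stays open until the data are seen. The conduct point comes down to asking which of two readings is meant, and the more natural one creates little conflict.

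**Conclusion.** No change to the plan is needed. Section 4.3 has a small gap in wording that analysts would fill sensibly: data collected before an adverse-event withdrawal are kept, as they are for withdrawal of consent or loss of capacity. The causal event is captured under the adverse-event reporting rules. Section 8.2 is not in conflict, and section 6 is only loosely in tension.

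Without such a withdrawal the effect on results is nil. With one after a usable visit, 1 of 11 participants or 1 of 21 meal records is affected. Any shift in the estimate beyond that count depends on assumed risks and assumed differences that the protocol does not supply, in a pilot of 10 people with no formal power calculation. The conclusion rests on two readings: that silence on adverse-event data is not exclusion, and that the bar on further information is aimed at people who choose to leave. If the second were wrong, the loss would be limited to the later course of an event already reported.

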5. ADVERSE EVENTS

5.1. DEFINITIONS

Adverse Event (AE): any untoward medical occurrence in a patient or clinical study subject.

Serious Adverse Event (SAE): any untoward medical occurrence or effect that:

- **Results in death**
- **Is life-threatening** – refers to an event in which the subject was at risk of death at the time of the event; it does not refer to an event which hypothetically might have caused death if it were more severe
- **Requires hospitalisation, or prolongation of existing inpatients' hospitalisation**
- **Results in persistent or significant disability or incapacity**
- **Is a congenital anomaly or birth defect**

Medical judgement should be exercised in deciding whether an AE is serious in other situations. Important AEs that are not immediately life-threatening or do not result in death or hospitalisation but may jeopardise the subject or may require intervention to prevent one of the other outcomes listed in the definition above, should also be considered serious.

5.2. REPORTING PROCEDURES

All adverse events should be reported. Depending on the nature of the event the reporting procedures below should be followed. Any questions concerning adverse event reporting should be directed to the Chief Investigator in the first instance.

4.3.1 Non serious AEs

All such events, whether expected or not, should be recorded- it should be specified if only some non-serious AEs will be recorded, any reporting should be consistent with the purpose of the trial end points.

4.3.2 Serious AEs

An SAE form should be completed and emailed to the Chief Investigator within 24 hours. However, relapse and death and hospitalisations for elective treatment of a pre-existing condition do not need reporting as SAEs.

All SAEs should be reported to the London Westminster Research Ethics Committee, where in the opinion of the Chief Investigator, the event was:

- 'related', ie resulted from the administration of any of the research procedures; and
- 'unexpected', ie an event that is not listed in the protocol as an expected occurrence

Reports of related and unexpected SAEs should be submitted within 15 days of the Chief Investigator becoming aware of the event, using the NRES SAE form for non-IMP studies. The Chief Investigator must also notify the Sponsor of all related and unexpected SAEs.

Local investigators should report any SAEs as required by their Local Research Ethics Committee, Sponsor and/or Research & Development Office.

Contact details for reporting SAEs

[contact]
CI email (and contact details below)
Email: [contact], attention [name]
Please send SAE forms to: [name]
[contact] (Mon to Fri 09.00 – 17.00)

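### Section 4.3.2 exempts death from SAE reporting although section 5.1 defines death as an SAE, so a death does not itself trigger the 24-hour form

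*Protocol*

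**What the plan says.** Section 5.1 gives five criteria that make an adverse event serious. The first is "Results in death", with no condition on cause or timing. The second, life-threatening, is explained as one that "refers to an event in which the subject was at risk of death at the time of the event".

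Section 5.2 opens with "All adverse events should be reported" and then directs the reader to the procedures beneath it, according to the type of event. Those procedures are numbered 4.3.1 (non-serious events) and 4.3.2 (serious events).

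Section 4.3.2 says "An SAE form should be completed and emailed to the Chief Investigator within 24 hours". The next sentence reads "However, relapse and death and hospitalisations for elective treatment of a pre-existing condition do not need reporting as SAEs". A new paragraph then begins "All SAEs should be reported to the London Westminster Research Ethics Committee" and limits this to events that the Chief Investigator judges related and unexpected. These have a 15-day limit, and the sponsor must also be notified of them.

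**The concern.** The most serious outcome the protocol defines is taken out of SAE reporting by the section meant to govern it. The study population is healthy adults, with the main chronic diseases excluded, so no underlying illness makes death an expected outcome and there is nothing to relapse from. Staff who followed section 4.3.2 as written could omit the SAE form for a death and would have followed the protocol in doing so.

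What is at stake is safety oversight: how quickly the Chief Investigator learns of a death and, depending on the reading, whether the ethics committee and the sponsor hear of a related one. No objective or outcome concerns safety, so the study's planned results are not affected.

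**Working it through.** The protocol gives no figure to reproduce here. The check is a comparison of the text, followed by simple arithmetic on exposure.

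**1. The rules side by side**

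| Place | Rule | Applied to a death |
|---|---|---|
| Section 5.1 | Death is an SAE criterion, unqualified | Serious |
| Section 5.2 | Every adverse event is reported, by the procedure for its type | To be reported; no deadline given here |
| Section 4.3.1 | Procedure for non-serious events | Does not apply |
| Section 4.3.2, form | SAE form to the Chief Investigator in 24 hours | Would apply |
| Section 4.3.2, exemption | Relapse, death and elective hospitalisation are not reported as SAEs | Removed |

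A death therefore keeps a general duty to report but loses the only procedure that supplies a form and a deadline.

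**2. Can the exemption be read more narrowly?** The phrase about elective treatment of a pre-existing condition fits hospitalisations only; it makes no sense applied to a death. The exemption for death is therefore unqualified, and no other section limits it by cause.

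**3. Effect on the committee and sponsor routes**

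- Reading A: the exemption concerns only the 24-hour form. The next paragraph starts again with all SAEs, and section 5.1 still makes a death an SAE, so a related and unexpected death goes to the committee and the sponsor. The 15-day clock, however, starts only when the Chief Investigator learns of the event, and the 24-hour form is the only timed step that ensures this.
- Reading B: an event that need not be reported as an SAE is outside that paragraph too. A related and unexpected death then misses both routes.

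The text does not settle which reading applies.

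**4. Exposure** (inputs from section 3.3: 10 participants, two visits, at most two hours per visit, and "involvement with the study will be up to 8 weeks")

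- Planned visits: 10 × 2 = 20. Observed time: 20 × 2 h = 40 h. Section 4.3 on withdrawal lets withdrawn participants be replaced, so 40 h is the total for the planned ten, not a strict upper limit.
- Per participant: 2 × 2 h = 4 h observed, against 8 × 168 h = 1,344 h of involvement if all 8 weeks are used. 4 / 1,344 = 0.30%.

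Section 6 adds "There will not be follow-up visits", only email contact. Nearly all of a participant's time in the study can thus pass away from the facility, where staff may see no earlier qualifying event before a death.

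**The case against.** The strongest counter-argument is that the life-threatening criterion fills the gap. It is not exempted, it does not require staff to witness anything, and an occurrence that ends in death will almost always have put the person at risk of death when it happened. Section 5.1 also lets medical judgement make an event serious. This has force: in practice many fatal events could still be reported on that ground. It does not remove the conflict, because a reader can equally apply the specific exemption for death first, and the protocol does not say which takes precedence.

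Second, a definition of seriousness and an exemption from reporting are different things. The same sentence exempts elective hospitalisation, which is also a narrowing of a listed criterion, and that is not disputed here. This is fair, but the hospitalisation exemption is bounded and its reason is evident. The exemption for death is unbounded and has no stated reason.

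Third, the loss of the committee and sponsor routes arises only on reading B, and local investigators must still report SAEs as their ethics committee, sponsor or research office requires. Both points stand. The local duty is itself worded in terms of SAEs, however, and its content lies outside the protocol.

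Finally, hours of observation do not measure the defect in a reporting clause. That is accepted: they show only that exposure is small and mostly unobserved.

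**Conclusion.** The contradiction is real, and section 4.3.2 is wrong as written. One of the five SAE criteria is set aside for the 24-hour form on both readings, and for the 15-day committee report and the sponsor notification on one of the two.

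The practical effect is small. A death is very unlikely among healthy adults attending two short meal visits; the protocol gives no rate, so this is a judgement rather than a calculated figure. The general duty to report adverse events, the life-threatening and emergency-hospitalisation criteria, and local reporting duties all remain.

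The conclusion assumes that the exemption is applied as worded. The mention of relapse suggests text carried over from a study in patients, but that is an inference and the conclusion does not depend on it. The point should be fixed because it concerns safety reporting and is easily put right.

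**What to change.** Amend the exempting sentence in section 4.3.2 by deleting its references to relapse and to death, so that only hospitalisation for elective treatment of a pre-existing condition stays exempt. The section 5.1 definition then governs the 24-hour form, the ethics-committee report and the sponsor notification alike. Sections 5.1, 5.2 and 4.3.2 agree, and the choice between readings A and B no longer arises.

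The cost is a one-line protocol amendment. It adds no procedure, visit or data item.
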